8.4.2.1 Mental Health, Minority stress Mechanisms, Universal Mechanisms

Analysis	In these models, we will assess whether Chinese ESTEEM iCBT will yield greater reduction in secondary outcomes (i.e., depression, anxiety, minority stress, and universal mechanisms) at the immediate post-intervention (4-month follow-up) timepoint and the 8-month follow-up. Mental health outcomes include depression symptoms (PHQ-9); Anxiety symptoms (GAD-7,); alcohol and substance use (AUDIT, DUDIT); and suicidality (SIDAS). Secondary minority stress outcomes include concealment motivation (LGBIS), acceptance concerns (LGBIS), internalized homonegativity (LGBIS). Secondary universal mechanism outcomes include emotion dysregulation (DERS), social support (MSPSS, LGBIS), and rumination (RRS).
----------	--

STATISTICAL ANALYSIS PLAN

Analysis population	All participants
Endpoint	Immediate post-intervention (4-month follow-up) and 8-month follow-up
Unit of analysis	Participant
Method of analysis	Depending on the outcome we will use repeated measures generalized linear mixed models (for continuous outcomes) and generalized linear mixed models with a logit link (for binary outcomes). We will use maximum likelihood estimation with contrasts to test condition x time comparisons at each relevant timepoint. We will test the best-fitting correlation structure, but based on our previous studies, expect it to be compound symmetrical. In the event of high skew or zero inflation, the appropriateness of modeling a negative binomial or Poisson distribution will be considered.
Handling of missing data	MAR assumption
Adjustment covariates	Adjustment for baseline covariates not balanced at randomization
Type I error	5% (2-sided)
Control of type I error	To control for the false discovery rate, we will apply a Bonferroni correction for each set of moderators (e.g., mental health, minority stress). Primary interpretation will focus on effect sizes.
Treatment effect estimate	Odds ratio with 95% confidence limits

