7.7 Handling of Missing Data

We will use an intent-to-treat analysis including all eligible cases. Maximum likelihood estimation will be employed, which is robust to missing data at followup.

8 Data/Specimen Handling and Record Keeping

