6.2 Sample Size Determination for the Primary Outcome

Assigning 60 YMSM to each condition (iCBT vs. self-monitoring) and accounting for 20% attrition, a liberal estimate based on our previous online RCT attrition of 0-17%, will provide \geq 80% chance of detecting a difference ($p < .05$) between the conditions of $d = .40$, which is lower than we found when comparing in-person ESTEEM to waitlist ($d = .59$ for CAS).²⁹ While we likely do not have power to detect changes in our biologic HIV/STI outcomes, including them 1)

STATISTICAL ANALYSIS PLAN

verifies study eligibility, 2) establishes self-testing protocols for our future research, and 3) promotes public health.

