8.3 Analysis of Primary Outcome: HIV-Risk Behavior (Condomless Anal Sex)

Analysis	Primary analysis of primary outcome: Number of past-30-day condomless anal sex (CAS) acts with primary or casual partners as measured by the Timeline Follow-Back at the 8-month follow-up assessment.
Analysis population	All randomized participants
Endpoint	8-month follow-up
Unit of analysis	Participant
Method of analysis*	We will use repeated measures generalized linear mixed models with maximum likelihood estimation to test whether receipt of ESTEEM iCBT vs self-monitoring affects changes in the number of past-30-day CAS with primary or casual partners from baseline to 8-month follow up. We will use a contrast to test condition x time comparisons. We will test the best-fitting correlation structure, but based on our previous studies, expect it to be compound symmetrical. In the event of high skew or zero inflation, the appropriateness of modeling a negative binomial or Poisson distribution will be considered.
Handling of missing data	MAR assumption
Adjustment covariates	Adjustment for baseline covariates not balanced at randomization
Type I error	5% (2-sided)
Control of type I error	None

STATISTICAL ANALYSIS PLAN

Treatment effect estimate	Odds ratio with 95% confidence limits
---------------------------	---------------------------------------

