8.4.3.1 Moderation Analyses of Treatment Efficacy

Analysis	In these models, we will examine baseline depression (PHQ-9), anxiety (GAD-7), and minority stressors including concealment motivation (LGBIS), acceptance concerns (LGBIS), and internalized homonegativity (LGBIS) as potential moderators of
----------	---

STATISTICAL ANALYSIS PLAN

	ESTEEM iCBT efficacy, hypothesizing that YMSM with higher baseline depression, anxiety, and minority stress benefit most.
Analysis population	All participants
Endpoint	Immediate post-intervention (4-month follow-up) and 8-month follow-up
Unit of analysis	Participant
Method of analysis	
For all moderators (i.e., depression, anxiety, concealment motivation, acceptance concerns, and internalized homonegativity), a linear mixed model analysis will be performed. Moderation analysis models will include terms for condition, time, moderator, Condition X Time, Condition X Moderator, Time X Moderator, and Condition X Time X Moderator. To probe significant three-way interactions, we will perform simple slopes analyses and differences in slopes will be compared using z-score transformations.³⁵
 
We will test the best-fitting correlation structure, but based on our previous studies, expect it to be compound symmetrical. In the event of high skew or zero inflation, the appropriateness of modeling a negative binomial or Poisson distribution will be considered.

Handling of missing data	MAR assumption
Adjustment covariates	Adjustment for baseline covariates not balanced at randomization
Type I error	5% (2-sided)
Control of type I error	To control for the false discovery rate, we will apply a Bonferroni correction for each set of moderators (e.g., mental health, minority stress). Primary interpretation will focus on effect sizes.
Treatment effect estimate	Odds ratio with 95% confidence limits

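### Gaussian outcomes are fitted by maximum likelihood with no degrees-of-freedom rule, so nominal 5% tests run at about 5.2-5.5% even with t tests; REML with small-sample degrees of freedom removes this at the cost of SAP wording

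*SAP*

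**What the plan says.** - **Secondary outcomes (SAP 8.4.2.1; same wording in 8.4.1):** "We will use maximum likelihood estimation with contrasts to test condition x time comparisons at each relevant timepoint". Tests are two-sided at 5% and estimates carry 95% limits. SAP 8.6 applies the same approach to the exploratory scales.
- **Primary outcome (SAP 8.3):** "repeated measures generalized linear mixed models with maximum likelihood estimation", with a negative binomial or Poisson distribution to be considered if the data are skewed or zero-inflated. Protocol 7.2 plans a negative binomial model for this outcome.
- **Missing data (Protocol 7.7):** "Maximum likelihood estimation will be employed, which is robust to missing data at followup".
- **Moderation (SAP 8.4.3.1):** a linear mixed model with no estimator named. "Moderation analysis models will include terms for condition, time, moderator" and all their two- and three-way products. When a three-way interaction is significant, simple slopes are examined and "differences in slopes will be compared using z-score transformations". Protocol 7.2.1 runs the moderator analyses through the models of 7.2, which use maximum likelihood.
- **Numbers (SAP 6.2):** "Assigning 60 YMSM to each condition (iCBT vs. self-monitoring) and accounting for 20% attrition".

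REML, Kenward-Roger, Satterthwaite and any other degrees-of-freedom rule are absent from both documents.

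**The concern.** In a Gaussian mixed model, maximum likelihood estimates the variance as though the fixed effects were known. The variance is therefore too small by roughly the factor (N - p)/N, where p is the number of fixed effects that bear on the contrast. A z reference would add a second error in the same direction, because it ignores that the variance is itself estimated. REML with Kenward-Roger or Satterthwaite degrees of freedom corrects both, and it is as valid as maximum likelihood under the SAP's missing-at-random assumption.

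At stake are the 95% intervals and 5% tests for continuous secondary, exploratory and moderation analyses. The shortfall is larger for moderator interactions, which use more fixed effects. There, significance also decides which interactions are probed, and moderation by minority stress is Aim 2 of the SAP.

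**Working it through.** **Inputs.** 120 randomised, 60 per arm, 20% attrition (SAP 6.2); 5% two-sided (SAP 8.4.2.1, 8.4.3.1); all participants analysed (same tables). Only the sample size and attrition are taken from 6.2; its power statement is not used.

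**1. Range for N.** 120 x (1 - 0.20) = 96 with follow-up; the upper end is all 120. The SAP also cites "our previous online RCT attrition of 0-17" per cent: 120 x 0.83 is about 100, inside this range.

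**2. Standard-error ratio, maximum likelihood to REML.** In change-contrast form the ratio is sqrt((N - p)/N), with p = 2 for an arm contrast (intercept, arm) and p = 4 for a moderator interaction (intercept, arm, moderator, product).

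**3. Actual test size.** Size = 2 x P(T > c x ratio), where T has N - p degrees of freedom and c is the 97.5% point of t or of z (1.96).

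| N | p | Ratio | SE too small by | Size, t reference | Size, z reference |
|---|---|---|---|---|---|
| 96 | 2 | sqrt(94/96) = 0.9895 | 1.0% | 5.24% | 5.54% |
| 96 | 4 | sqrt(92/96) = 0.9789 | 2.1% | 5.49% | 5.81% |
| 120 | 2 | sqrt(118/120) = 0.9916 | 0.8% | 5.19% | 5.43% |
| 120 | 4 | sqrt(116/120) = 0.9832 | 1.7% | 5.39% | 5.64% |

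The plan's nominal 5.0% is recovered when the ratio is 1 and c comes from t, which is REML with t degrees of freedom.

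**4. Compound symmetry, the structure the SAP expects.** With three visits the within-person part has 2N contrasts and 4 fixed effects (8 with a moderator). At N = 96 the ratios are sqrt(188/192) = 0.9895 and sqrt(184/192) = 0.9789, as before. The t rates are essentially unchanged (5.24% and 5.50%). The z rates fall to 5.39% and 5.66%, and at N = 120 to 5.31% and 5.52%.

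**5. Simulation under no effect.**
- Change-contrast form, 60,000 trials per setting: maximum likelihood with t 5.21-5.51%, with z 5.46-5.81%; REML with t 4.99-5.05%.
- Compound symmetry, 15,000 trials per setting, assumed within-person correlation 0.5, Monte Carlo standard error 0.18 points: maximum likelihood with t 5.03-5.47%, with z 5.15-5.65%; REML with t 4.78-5.11%. The 5.03% is the arm contrast with 120 randomised and 20% dropout, so for that contrast the excess may be smaller than the formula gives.

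**6. Sensitivity to covariates.** The SAP allows adjustment for unbalanced covariates, which raises p. Assuming three are added to the moderator form at N = 96 (p = 7), the ratio is sqrt(89/96) = 0.9629 and the size is 5.9% with t or 6.2% with z.

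**7. Cost in precision.** Against maximum likelihood with t, intervals widen by 1/0.9916 - 1 = 0.8% up to 1/0.9789 - 1 = 2.2%. Against maximum likelihood with z at N = 96 and p = 4, they widen by 1.986/(1.960 x 0.9789) - 1 = 3.5%.

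**The case against.** The strongest reply is that this hardly matters. Maximum likelihood is a standard, valid choice under missing at random. Without added covariates the excess is under one percentage point. SAP 6.3 and the Type I error rows say that secondary and moderation results will be read mainly through effect sizes. The primary outcome is a count, for which Protocol 7.2 plans a negative binomial model, so REML would not apply to it. The SAP also allows count distributions for skewed scales. All of this stands, and it keeps the point minor. It does not remove the point: effect sizes are read with their intervals, those intervals are slightly too narrow, and significance still decides which interactions are probed.

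A reader might also infer that all these tests use z. On that reading the interaction test would run at about 2.1% against a Bonferroni level of 0.05/3 = 1.67%, roughly 27% more false positives. The documents do not support this. They give z only to the comparison of simple slopes after an interaction is already significant. They do not give it to the interaction test or to the condition-by-time contrasts. With t the figure is 1.9%. The divisor of 3 also fits only the three minority-stress moderators; the depression and anxiety pair would use 2.

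Nor is 96 the stated analysis set. It is the planned number with follow-up, and the SAP analyses all participants. The bias persists at 120, slightly smaller.

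**Conclusion.** The point holds as a small, one-directional error confined to Gaussian models. Standard errors are about 0.8-2.1% too small, and with t tests a nominal 5% test runs at about 5.2-5.5%. The z range of about 5.3-5.8% applies only if software defaults to z, which the SAP leaves open for everything except the simple-slopes comparison.

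The figures assume 96 to 120 participants contributing, no added covariates, and maximum likelihood carried into the moderation models from the protocol. They do not show that maximum likelihood mishandles the missing data, and they say nothing about the count or binary models. The consequence falls mainly on secondary, exploratory and moderation analyses. It is worth correcting because it costs almost nothing, not because it is likely to change a conclusion.

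**What to change.** - In SAP 8.4.2.1, 8.4.3.1 and 8.6, and in 8.3 and 8.4.1 wherever a Gaussian model is fitted, specify REML with Kenward-Roger or Satterthwaite degrees of freedom and t-based tests and intervals.
- In 8.4.3.1, name the estimator and replace the z comparison of simple slopes with the corresponding contrast from the fitted model.
- Keep maximum likelihood for the negative binomial, Poisson and logit models, and say so.

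The cost is SAP wording and intervals about 1-4% wider. No participants, data or new software are needed: SAS and R, both named in SAP 8.1, support REML with these degrees of freedom.

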8.4.3 Moderation Analyses of Treatment Efficacy

Moderation analyses of treatment efficacy will examine

8.4.3.1 Moderation Analyses of Treatment Efficacy

Analysis	In these models, we will examine baseline depression (PHQ-9), anxiety (GAD-7), and minority stressors including concealment motivation (LGBIS), acceptance concerns (LGBIS), and internalized homonegativity (LGBIS) as potential moderators of
----------	---

STATISTICAL ANALYSIS PLAN

	ESTEEM iCBT efficacy, hypothesizing that YMSM with higher baseline depression, anxiety, and minority stress benefit most.
Analysis population	All participants
Endpoint	Immediate post-intervention (4-month follow-up) and 8-month follow-up
Unit of analysis	Participant
Method of analysis	
For all moderators (i.e., depression, anxiety, concealment motivation, acceptance concerns, and internalized homonegativity), a linear mixed model analysis will be performed. Moderation analysis models will include terms for condition, time, moderator, Condition X Time, Condition X Moderator, Time X Moderator, and Condition X Time X Moderator. To probe significant three-way interactions, we will perform simple slopes analyses and differences in slopes will be compared using z-score transformations.³⁵
 
We will test the best-fitting correlation structure, but based on our previous studies, expect it to be compound symmetrical. In the event of high skew or zero inflation, the appropriateness of modeling a negative binomial or Poisson distribution will be considered.

Handling of missing data	MAR assumption
Adjustment covariates	Adjustment for baseline covariates not balanced at randomization
Type I error	5% (2-sided)
Control of type I error	To control for the false discovery rate, we will apply a Bonferroni correction for each set of moderators (e.g., mental health, minority stress). Primary interpretation will focus on effect sizes.
Treatment effect estimate	Odds ratio with 95% confidence limits

